Grade 3 or Grade 4 – severe or life-threatening	
• Grade 3: Prolonged (for example, not rapidly responsive to• Decrease the Bintrafusp Alfa (M7824) infusion rate by 50% and monitor closely for any worsening.• The total infusion time for Bintrafusp Alfa (M7824) should not exceed 120 minutes• Stop Bintrafusp Alfa (M7824) infusion.• Resume infusion at 50% of previous rate once infusion-related reaction has resolved or decreased to at least Grade 1 in severity, and monitor closely for any worsening• Stop the Bintrafusp Alfa (M7824) infusion immediately and disconnect infusion tubing from the subject.

- symptomatic medication and / or brief interruption of infusion); recurrence of symptoms following initial improvement; hospitalization indicated for clinical sequelae.
- Grade 4: Life-threatening consequences; urgent intervention indicated.
- Subjects have to be withdrawn immediately from Bintrafusp Alfa (M7824) treatment and must not receive any further Bintrafusp Alfa (M7824) treatment

IV = intravenous; NCI-CTCAE = National Cancer Institute – Common Terminology Criteria for Adverse Event; NSAIDs = nonsteroidal anti-inflammatory drugs

Additional Modifications for Subjects with Grade 2 Infusion-related Reactions

If, in the event of a Grade 2 infusion-related reaction that does not improve or worsens after implementation of the modifications indicated in **Table 2** (including reducing the infusion rate by 50%), the Principal Investigator may consider treatment with corticosteroids and the infusion of BINTRAFUSP ALFA should be stopped for that day. At the next infusion, the Principal Investigator may consider the addition of H2-blocker antihistamines (for example, famotidine or ranitidine), in addition to premedication, for select subjects. However, prophylactic steroids are NOT permitted. If the subject has a second infusion-related reaction Grade ≥ 2 on the slower infusion rate, with or without the addition of further medication to premedication, the infusion should be stopped and the investigator may consider withdrawal of this participant from the study.

Immune-Related Adverse Events

For reporting irAE severity/toxicity grading, refer to CTCAE v.5 toxicity grading system.

For treatment management of irAE per CTCAE v.5 criteria, refer to American Society of Clinical Oncology (ASCO) Clinical Practice Guidelines and National Comprehensive Cancer Network irAE Management Guidelines. Refer to Appendix 6 and 7.

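### In Section 6.2.3, one infusion-related reaction can fall both under Table 2's permanent withdrawal from bintrafusp alfa and under a paragraph that goes on to the next infusion

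*Combined protocol and SAP*

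**What the plan says.** Both instructions are in Section 6.2.3.

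**Table 2.** The last row is labelled "Grade 3 or Grade 4 – severe or life-threatening". Its action is mandatory and permanent: "Subjects have to be withdrawn immediately from Bintrafusp Alfa (M7824) treatment and must not receive any further Bintrafusp Alfa (M7824) treatment". The row describes Grade 3 in two fragments: "Grade 3: Prolonged (for example, not rapidly responsive to" symptomatic medication or a short interruption, and "recurrence of symptoms following initial improvement; hospitalization indicated for clinical sequelae". Grade 2 is described as a reaction that settles promptly with symptomatic treatment. Its action is to stop, then restart at half the previous rate once the reaction has resolved or fallen to Grade 1.

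**The paragraph below the table.** It is headed "Additional Modifications for Subjects with Grade 2 Infusion-related Reactions" and has two triggers.

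- First, a Grade 2 reaction that fails to improve or gets worse after the Table 2 measures, including halving the rate. The action is that "the infusion of BINTRAFUSP ALFA should be stopped for that day". The text then says what premedication may be added at the next infusion.
- Second, another reaction of Grade 2 or higher on the slower rate. The action is that "the infusion should be stopped and the investigator may consider withdrawal of this participant from the study".

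**The concern.** Table 2 leaves no discretion at Grade 3 or 4. The paragraph's first trigger stops a single day's infusion and assumes another will follow, yet it puts no upper limit on how far the reaction may have worsened. Its second trigger is open-ended upwards and makes withdrawal optional.

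Two things are at stake. A patient whom Table 2 excludes from further drug could be given another dose by staff who follow the paragraph; bintrafusp alfa is given every 2 weeks (Section 6.1.1), so that dose would normally be close. In addition, similar reactions could be recorded as permanent discontinuation in one patient and as a one-day interruption in another, which blurs the exposure and discontinuation data from a study meant to characterise the safety of the combination.

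**Working it through.** No figure in the plan depends on this point, so there is nothing to recompute. The check is a comparison of texts.

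| Reaction | Table 2 | Paragraph below Table 2 |
|---|---|---|
| Grade 2, not improving or worsening after the Table 2 measures | Permanent withdrawal from the drug if the reaction is now Grade 3 or 4 | Stop for that day; next infusion described; no grade limit |
| Second reaction on the slower rate, Grade 3 or 4 | Permanent withdrawal from the drug | Stop; withdrawal from the study may be considered |
| First reaction already at Grade 3 or 4 | Permanent withdrawal from the drug | Not addressed |

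**Step 1: can a first-trigger reaction be Grade 3?** It can, by two routes.

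- *Worsening.* A Grade 2 reaction that rises by one grade is Grade 3. The sentence does not name the grade reached, so this overlap is by implication.
- *Table 2's own definitions.* Grade 2 requires a prompt response to treatment. A reaction that has not improved after interruption and a halved rate no longer fits that description, and it can fit the Grade 3 wording on slow response. If the infusion was restarted only after the reaction had fallen to Grade 1, symptoms that return can fit the Grade 3 wording on recurrence after improvement. This route does not depend on how the word for worsening is read.

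In either case the table ends bintrafusp alfa and the paragraph proceeds to another infusion. These outcomes are incompatible.

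**Step 2: does the second trigger include Grades 3 and 4?** It does explicitly, because Grade 2 or higher has no upper bound. The two texts have different objects, however. Table 2 withdraws the patient from bintrafusp alfa *treatment*; the paragraph speaks of withdrawal from the *study*. Sections 8.13 and 8.15 treat these as different things, since patients who stop drug are encouraged to complete visits and must be followed for outcome or survival. A site could end the drug under Table 2 and separately consider study withdrawal under the paragraph. The paragraph does not itself direct a dose after a second reaction. This limb is an ambiguity and not a direct opposition.

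**Step 3: does another section settle it?** None does. Special Precautions (in Section 7.0) stops the infusion at Grade 2 or higher and refers back to Section 6.2.3. Section 6.1 also refers there for changes to the infusion rate. The opening of Section 6.2.3 sends the reader to a Table 6 for management of these reactions, but the only other mention of a Table 6 concerns contraception, in Appendix 4.

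**Step 4: does DLT status change?** It does not. Section 9.1 defines an extracranial DLT by grade (3 or higher), relatedness and the 4-week window, with listed exceptions. Whether the drug is later withdrawn plays no part.

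**The case against.** The strongest reply is that the heading confines the paragraph to Grade 2 reactions and calls its content additional, so it supplements Table 2 and exempts nothing. Symptoms can worsen within Grade 2. Section 10.1 requires every change of grade to be recorded, so a reaction that reaches Grade 3 is a Grade 3 reaction and meets an absolute rule in the table.

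This is a reasonable reading, and it would remove the conflict if the document stated it. The heading, however, describes the reaction that starts the sequence. The text below it reaches to worsening and, for the second reaction, to every grade from 2 upward. No sentence says which text prevails. The reply also leaves untouched the overlap created by Table 2's own Grade 3 wording, which can cover a reaction that has simply not improved.

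The reply is right about the second reaction: withdrawal from the study and withdrawal from treatment can both be honoured. A reader might infer that the paragraph permits further dosing after a second Grade 3 or 4 reaction. It does not say that; it only makes study withdrawal discretionary.

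The columns of Table 2 are scrambled in the extracted text. That is not a fault of the plan, and it does not help the reply: the permanent-withdrawal action plainly belongs to the Grade 3 or 4 row.

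**Conclusion.** The point holds for the first trigger. One event can fall under both permanent withdrawal and continued dosing. It rests on two readings: that the paragraph's silence on an upper grade is a real gap, and that Table 2's Grade 3 description means what it says. For the second trigger the fault is narrower: a mandatory withdrawal from treatment sits beside a discretionary withdrawal from the study, and nothing explains how they relate.

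The consequence is possible re-exposure after a severe reaction, together with inconsistent discontinuation. Its size cannot be estimated. The protocol calls these reactions common with monoclonal antibodies but gives no rate, and the affected subset is limited to Grade 2 reactions already managed under Table 2 and second reactions on the slower rate. A first reaction at Grade 3 or 4 falls under Table 2 alone. If withdrawal were taken to mean leaving the study and follow-up ended, each such patient would be 1/30 = 3.3% of the 30 planned at the RP2D, in a phase II part with overall survival as a primary endpoint.

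A reader might also infer that phase I DLT counts depend on which text is followed. Section 9.1 does not support that. No endpoint definition, sample size or analysis rule changes.

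**What to change.** Reconcile Table 2 with the paragraph beneath it so that each grade of a non-improving, worsening or second infusion-related reaction leads to one stated action. State also, wherever withdrawal is mentioned, whether it is from bintrafusp alfa treatment or from the study. Which action applies at each grade is for the sponsor to decide; this review takes no position on it.

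The cost is one or two sentences in Section 6.2.3. No change to the sample size, the schedule of assessments or the analysis is needed.

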6.2.4 SRT AND DOSE INTERRUPTIONS

Patients that have to hold systemic therapy to receive SRT are allowed to resume therapy within 6 weeks of holding therapy if they meet treatment safety parameters.

6.2.5 RESUMPTION OF TREATMENT AFTER DOSE DELAY

Patients may resume therapy at the same doses after dose interruption as long as they continue to meet the treatment safety parameters.

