	
 • In case of alternative explanations, hold study treatment until the event recovers to Grade ≤ 1
Grade 4	
 • Treatment must be permanently discontinued if no alternative explanation is identified.
Tumor Bleeding	
Grade ≥ 2	
 • Study treatment must be held till the event recovers to Grade ≤ 1 • Permanently discontinue treatment if the Investigator considers the participant to be at risk for additional severe bleeding.

Ocular toxicity

If a subject experiences Retinal Vein Occlusion the pimasertib treatment must be immediately stopped. Appropriate follow-up and treatment measures must be taken by the treating ophthalmologists.

If a subject shows a symptomatic serous retinal detachment: Withhold treatment for ≤ 3 weeks, if improved to grade 0/1, resume at same dose level. If not improved, resume at the lower dose level or permanently discontinue pimasertib treatment. Management should be discussed with Principal Investigator and ophthalmologist.

Elevation of Serum Creatine Phosphokinase

Subjects should be advised to immediately report any muscle pain, tenderness or weakness, or any macroscopic myoglobinuria (tea-colored urine). Subject-reported muscle symptoms or urine discoloration should be investigated with CPK measurements and urinalysis for myoglobinuria.

CPK measurement should be at screening and every 4 weeks; at any time for symptomatic patients. Assess with differentiation if irAE or due to Pimasertib; including DD presence/absence of further symptomatic findings: full history (including commeds), exercises, training, muscular injury, muscular injections, CPK isoenzymes, and etc.

CPK increase G4: Withhold pimasertib treatment for ≤ 3 week

Any CPK elevation and myalgia: If improved to grade ≤ 3 , resume at lower dose level, if not improved within 3 weeks, permanently discontinue pimasertib treatment.

Dehydration

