 - For **Grade 3-4** events, treat with intravenous corticosteroids for 24 to 48 hours.
 - When symptoms improve to Grade 1 or less, a steroid taper should be started and continued over no less than 4 weeks.
- **Renal Failure or Nephritis:**
 - For **Grade 2** events, treat with corticosteroids.
 - For **Grade 3-4** events, treat with systemic corticosteroids.
 - When symptoms improve to Grade 1 or less, steroid taper should be started and continued over no less than 4 weeks.
- **Ocular reactions:**
 - Visual disturbances: for Grade 2 events, pimasertib should be discontinued until full resolution of the event and recovery of vision, assuming resolution of the event within 2 weeks to Grade 1 or less.
 - In case of visual symptoms but without vision loss, the treatment will not be discontinued.
- **Skin reactions:**
 - Early introduction of oral tetracyclines and medium to high potency topical treatment (such as 1% hydrocortisone cream with moisteriser) should be initiated in case of Grade 1 or 2 skin reaction. The dose of the investigational treatment should not be decreased.
 - If a subject experiences a severe skin reaction (Grade ≥ 3), pimasertib therapy must be interrupted and may be resumed at the original dose when the reaction has resolved to Grade 1 or 2. In case of second or third occurrence of severe skin reaction pimasertib therapy must again be interrupted. Treatment may only resume at a lower dose level (45 mg BID after the second occurrence and 30 mg BID after the third occurrence) if the reaction has resolved to Grade 1 or 2. In case of further recurrence another dose reduction may be proposed.

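### Section 6.2.5 permits restarting at an unchanged dose with no stated exception, which conflicts with the CPK rule and the repeat skin-reaction rule; the CPK wording and the skin-rule dose levels also need reconciling

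*Combined protocol and SAP*

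**What the plan says.** The general rule is in Section 6.2.5: "Patients may resume therapy at the same doses after dose interruption as long as they continue to meet the treatment safety parameters". Section 6.2.4, just before it, uses the same condition for radiotherapy holds, after which patients are "allowed to resume therapy within 6 weeks of holding therapy if they meet treatment safety parameters". Neither section says what those parameters are or where to find them.

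The toxicity-specific rules are elsewhere:

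- **CPK (Section 6.2.3).** One line reads "CPK increase G4: Withhold pimasertib treatment for ≤ 3 week". The next reads "Any CPK elevation and myalgia: If improved to grade ≤ 3 , resume at lower dose level, if not improved within 3 weeks", and failure to improve leads to permanent discontinuation.
- **Symptomatic serous retinal detachment (Section 6.2.3).** After a hold of up to 3 weeks, improvement to grade 0/1 allows the same dose level. Otherwise: "If not improved, resume at the lower dose level or permanently discontinue pimasertib treatment".
- **Grade 3 or higher skin reaction (Section 8.11).** After the first occurrence the original dose may be resumed. After the second or third, "Treatment may only resume at a lower dose level", given as 45 mg BID and then 30 mg BID.

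Section 6.2.1 allows assigned pimasertib doses of 30, 45 or 60 mg BID.

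**The concern.** A general permission to restart at an unchanged dose, with no exception, stands beside specific rules that require a reduction. Staff who consult 6.2.5 and staff who consult 6.2.3 or 8.11 can restart the same patient at different doses, and each can point to protocol text. Nothing in the protocol says which passage takes precedence.

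Two things are at stake. The first is safety: one section permits re-exposure at a dose that another excludes. The second is interpretation: pimasertib is the only agent whose dose varies between levels (Sections 3.0 and 9.1), and Section 9.2 pools 30 patients as treated at the RP2D. If restarts after toxicity are handled inconsistently, later exposure and longer-term tolerability in that group depend partly on which section was read.

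**Working it through.** The plan gives no figure to reproduce here. The check compares texts, with a little arithmetic on dose levels.

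**Step 1. Each resumption branch against 6.2.5.**

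| Branch | Section | Resumption dose stated | Against 6.2.5 |
|---|---|---|---|
| CPK, improved to grade ≤ 3 | 6.2.3 | lower level | conflicts |
| Retinal detachment, improved to grade 0/1 | 6.2.3 | same level | agrees |
| Retinal detachment, not improved | 6.2.3 | lower level or permanent stop | weak conflict |
| Skin, first occurrence | 8.11 | original dose | agrees |
| Skin, second occurrence | 8.11 | lower level only | conflicts |
| Skin, third occurrence | 8.11 | lower level only | conflicts |

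The retinal branch without improvement is only a weak conflict, because an unresolved detachment might itself fail the undefined safety parameters.

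**Step 2. Size of a one-level difference.** Inputs are the dose levels in Section 6.2.1.

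- From 60 mg BID: (60 − 45)/60 = 25%.
- From 45 mg BID: (45 − 30)/45 = 33%.
- From 30 mg BID: no lower level is listed, so the instruction to go down a level has no defined target.

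**Step 3. The CPK lines on their own terms.** The only stated hold trigger is Grade 4. The resumption line opens with "Any CPK elevation and myalgia", which read literally covers Grades 1 to 4. Its condition of grade ≤ 3 is then already true at onset for three of those four grades. That counts grades, not patients. If g4 is the share of covered patients at Grade 4, the share meeting the condition at onset is 1 − g4. The documents give no on-treatment CPK grade frequencies, so g4 is an assumption:

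| Assumed g4 | Share at grade ≤ 3 at onset |
|---|---|
| 10% | 90% |
| 25% | 75% |
| 50% | 50% |
| 75% | 25% |

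If the two lines are instead read as one Grade 4 rule, the share is 0%, but then the opening words about any elevation with myalgia do not fit.

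**Step 4. The skin-rule levels against the assigned dose.**

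| Assigned dose (BID) | Second occurrence, 45 mg | Third occurrence, 30 mg |
|---|---|---|
| 60 mg | lower | lower |
| 45 mg | same as assigned | lower |
| 30 mg | above assigned | same as assigned |

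The named steps are both reductions only for a patient who starts at 60 mg BID. For the other two permitted doses, the requirement for a lower level and the milligram figures beside it disagree.

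**The case against.** The best defence is that 6.2.5 is permissive and conditional. It says patients may restart at the same dose, not that they must, so a site can obey it and a stricter specific rule together. It also follows the radiotherapy hold rule and shares its condition, and Section 6.2.10 extends those criteria to neurosurgery, so it may have been meant only for such holds. The undefined parameters might be intended to bring in the toxicity rules.

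Part of this stands. A reader might infer that 6.2.5 applies to every interruption whatever its cause; the text does not say so. A reader might also infer that it contradicts the retinal and skin rules as a whole; it does not, since one branch of each agrees with it. The narrower intention remains a guess, however. Section 6.2.5 has its own general heading, radiotherapy holds already have Section 6.2.4, and no text limits 6.2.5 or gives the specific rules precedence. As worded, the safety parameters decide whether a patient may restart at the same dose; they do not select a different one. Permission to use the same dose is still incompatible with a rule that allows only a lower one.

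On CPK, it is fair to say that a patient who stays at Grade 2 has not improved, and that the two lines may be one rule split by layout. That supports calling the wording ambiguous. It does not settle which reading applies.

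On impact, the RP2D decision and the toxicity stopping rules rest on DLTs at 4 weeks (Sections 9.1 and 9.2), and the pill diary in Appendix 10 records doses taken. Restarts after a hold would mostly affect later exposure, which can be reconstructed.

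**Conclusion.** The inconsistency is real and should be corrected. Section 6.2.5 conflicts with three of six resumption branches (CPK, and the second and third severe skin reactions), fits poorly with one, and agrees with two. Where a lower listed level exists, a one-level difference is 25% or 33% of the pimasertib dose. The CPK entry and resumption conditions do not match on either reading, and the skin-rule levels do not work for every permitted assigned dose.

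Two stronger readings are not supported. A reader might infer that most patients covered by the CPK rule already meet its resumption condition. That needs g4 below 50% and the literal reading, and the documents establish neither. A reader might also infer that the RP2D selection is undermined. With DLTs assessed at 4 weeks and doses recorded, the documents support only a concern about safety on restart and about interpreting later exposure. How many patients would be affected is unknown, because no event rates are given. This review takes no view on which dose rule is right.

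**What to change.** The sponsor should:

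1. reconcile Sections 6.2.3, 6.2.5 and 8.11, and state which passage governs a restart after a toxicity-related hold;
2. tie the treatment safety parameters in 6.2.4 and 6.2.5 to criteria stated in the protocol;
3. reword the CPK lines so that the patients covered, the hold condition and the resumption condition are consistent with each other;
4. make the skin-rule dose levels, and every instruction to go to a lower level, consistent with the assigned doses that Section 6.2.1 permits.

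The choice of doses and thresholds belongs to the sponsor. The cost is a short wording amendment. No added tests are needed, since CPK is already measured at screening and every 4 weeks.

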6.2.6 CONCOMITANT AND EXCLUDED THERAPIES

Steroids are allowed to manage AEs as described in protocol. Medications or vaccinations specifically prohibited in the exclusion criteria (See section 5.2) are not allowed during the ongoing trial. The following are also prohibited and are not allowed:

- Any traditional Chinese medication used as anticancer treatment (regardless of the type of cancer) is prohibited. Traditional Chinese medication for indications other than anticancer treatment, such as supportive care, may be administered at the discretion of the Investigator.
- Herbal remedies with immunostimulating properties (e.g., mistletoe extract) or known to potentially interfere with major organ function (e.g., hypericin).

If there is a clinical indication for any medication or vaccination specifically prohibited during the trial, discontinuation from trial therapy or vaccination may be required. The final decision on any supportive therapy or vaccination rests with the principal investigator and/or the subject's primary physician. However, the decision to continue the subject on trial therapy or vaccination schedule requires the mutual agreement of the principal investigator, and the subject.

